5.2 Statistical Analysis of Research Data

5.2.1 Analysis Variables

The analysis variables include subject characteristics at baseline, laboratory indicators, auxiliary examination indicators (electrocardiogram; echocardiogram), and endpoint event indicators.

5.2.2 Analysis Populations

All patients who meet the screening criteria and commence treatment with lipoic acid capsules should be included in the Safety Population (SP). The analysis of the primary endpoint and other endpoint was based on the FAS dataset (Full Analysis Set). The FAS set is defined as the set that adheres to the ITT (Intent-to-Treat) principle with the additional condition that the investigational drug has been used for at least one month, allowing for reasonable exclusions and enabling the reflection of the investigational drug's efficacy and safety to the greatest extent possible. Per-protocol analysis (PP set):Refers to subjects who do not have serious protocol violations in terms of inclusion and exclusion

criteria, treatment, and measurement of main indicators. The analysis was performed after the population withdrew from the study.

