Withdrawal criteria: 1. The participant themselves requests to withdraw from the trial; 2. The participant experiences an intolerable adverse event, or an adverse event that, in the investigator's opinion, necessitates withdrawal from the study; 3. The participant is unable to adhere to the study protocol for treatment, demonstrates poor compliance, or is deemed by the physician to be unsuitable for continued participation in the study group.

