3.4 Investigational Drugs

3.4.1 Investigational Medicinal Products:

Investigational Drug: Lipoic Acid Capsules

Placebo: Contains starch as the inert ingredient, with an identical appearance to the investigational drug

3.4.2 Dosage Form, Dose, Route of Administration, Administration Method, Frequency of Administration, and Treatment Duration

Dosage Form: 100mg capsules

Dose: 600mg per day

Route of Administration: Oral

Frequency of Administration: 200mg per dose, administered three times daily

Treatment Duration: 24 months

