3.4.3 Packaging and Labeling

For research only	Protocol ID: 2018-120
Lipoic Acid Capsules for Clinical Trial Use	
Drug ID: _____	Name Abbreviation: _____
Dispensing Date: _____	
Dosage and Administration: Take 2 capsules at a time, three times daily.	
Packaging: Each bottle contains xx capsules.	
Storage: Keep the container tightly closed. Expiration Date: XXXX	
All unused medication, along with its original packaging, must be returned to the investigator.	
Keep out of reach of children	

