3.5 Research Procedures

3.5.1 Screening and Enrollment Period

At the hospital's heart failure outpatient clinic and inpatient ward, consecutive patient screening was initiated based on inclusion and exclusion criteria. Detailed information about the study objectives, significance, and procedures was provided to patients. Their consent was obtained, and informed consent forms were signed.

Eligible patients were randomized in a 1:1 ratio to either the lipoic acid capsule group or the control group. Patients continued their current optimized medications and additionally received the study drug.

ALA Group:

Standard treatment for post-myocardial infarction heart failure + lipoic acid capsules (1 capsule/dose, 3 times/day for the first week, escalated to 2 capsules/dose, 3 times/day thereafter, swallowed with warm water).

Placebo Group:

Standard treatment for post-myocardial infarction heart failure + placebo (1 capsule/dose, 3 times/day for the first week, escalated to 2 capsules/dose, 3 times/day thereafter, swallowed with warm water).

Concomitant Standard Therapy (Medications and Devices):

Patients should adhere to current treatment guidelines[29], with therapies tailored by clinicians based on individual conditions. Risk factors such as blood glucose, blood pressure, and lipids should be controlled. Patients should receive dietary guidance for cardiac health (e.g., low-salt diet) and lifestyle modifications, including weight monitoring, physical exercise, smoking cessation, and alcohol restriction. Device-based therapies, including but not limited to stent implantation, may be administered according to current guidelines and patient conditions.

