4.4 Risk Prevention and Management

The investigator should assess the clinical significance of abnormal laboratory results and provide possible explanations. Laboratory abnormalities resulting from previously reported adverse events should

also be recorded as adverse events in the Adverse Event Form. Laboratory abnormalities with clinical significance that meet one or more of the following criteria should be recorded as independent diagnoses in the Adverse Event section of the CRF (excluding abnormalities resulting from previously reported adverse events):1.Accompanied by clinical symptoms ; 2.Leading to changes in clinical medication ; 3.Requiring modification of concomitant therapy.

For unexplained abnormal laboratory values, repeat testing should be performed, and follow-up should continue until the value returns to the normal reference range or baseline, and/or a reasonable explanation is found. If a clear explanation is identified, it should be documented on the CRF.

During the clinical trial, investigators should closely monitor the occurrence of serious adverse events. Upon the occurrence of a serious adverse event, necessary measures should be taken first to ensure the safety of the subject, followed by reporting to the sponsor, contract research organization (CRO), and the ethics committee of the center within 24 hours.

All safety follow-up visits will be conducted 15 days after the end of the study visit. For subjects who withdraw prematurely, safety follow-up will also be conducted 15 days after the end of the study visit, unless the investigator deems it necessary for the subject to return to the hospital for follow-up measurements due to persistent adverse events at the end of treatment or clinically significant abnormalities in laboratory tests or vital signs. Safety follow-up may be conducted via telephone.

五、 Statistic Method

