5.2.3 Statistical Methods

All statistical analyses were performed with R version 4.0.2. Normally distributed continuous variables were reported as the mean \pm SD, and non-normally distributed continuous variables were expressed as the median and interquartile range. Categorical data were expressed as absolute values and percentages and analyzed using the chi-square or Fisher's exact test. The Student's t-test or Wilcoxon rank-sum test was performed to determine differences between groups. Survival analyses were based on the time to the first event. The cumulative incidence of the time-to-event end points is expressed as Kaplan-Meier curves over 24 months after randomization. Cox proportional hazard models were used to estimate HR and 2-sided 95% CI. A linear mixed-effects model was used to analyze the differences in changes of LVEF and 6MWD between the ALA group and the placebo group, with study centers included as random effects. Subgroup analysis was performed for age (whether \leq 65 years old), sex, smoking status, past medical history (hypertension, diabetes mellitus, atrial fibrillation), NYHA functional class, NT-proBNP levels, LVEF (whether \leq 30%), and whether the patient received triple therapy.

The analysis of safety and efficacy was performed in full analysis set (FAS) adhering to the intention-to-treat principle. The type I error rate (2-sided α) was set at 0.05.

六、Ethics

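### Safety is analysed only in patients with at least one month of drug use, so early stops and deaths drop out, and the defined Safety Population is never used

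*Protocol*

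**What the plan says.** Section 5.2.2 of the protocol defines three sets. The first is for safety: "All patients who meet the screening criteria and commence treatment with lipoic acid capsules should be included in the Safety Population (SP". The second is the FAS, described as intention to treat "with the additional condition that the investigational drug has been used for at least one month". The third is a per-protocol set. Section 5.2.3 then assigns the analyses: "The analysis of safety and efficacy was performed in full analysis set (FAS", again described as intention to treat. The Safety Population is named only in 5.2.2, and no analysis is assigned to it.

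Other parts of the protocol bear on this:

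- Section 3.2, withdrawal criteria, gives as one ground: "The participant experiences an intolerable adverse event".
- Section 3.5.1 schedules a dose step in both arms: "1 capsule/dose, 3 times/day for the first week, escalated to 2 capsules/dose, 3 times/day thereafter".
- Section 3.4.1 lists the comparator apart from the investigational drug: "Placebo: Contains starch as the inert ingredient". The label in 3.4.3 nevertheless reads "Lipoic Acid Capsules for Clinical Trial Use".
- Section 4.4 follows up early leavers: "For subjects who withdraw prematurely, safety follow-up will also be conducted 15 days after the end of the study visit".
- Section 5.1 names safety, with efficacy, as a purpose of the pilot, and says its data are to inform a larger randomised trial.

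**The concern.** A safety set normally contains everyone who took any study medication, because the patients who tolerate a drug least are the ones who stop early. Here the comparison is limited to patients who stayed on drug for a month. Someone who withdraws in week 2 for an intolerable adverse event is left out because of that event. Membership is decided after randomisation by something treatment can influence, so the two arms compared are no longer those that were randomised.

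The first month also matters on the protocol's own account. The dose step after week 1 falls within it, and section 3.4.4 singles out the start of treatment for attention to blood glucose. At stake is whether the pilot gives the later trial a fair picture of early tolerability. The stated analysis can understate early harm in either arm, and it cannot show a permanent first-month stop for an adverse event.

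**Working it through.** **Who enters which set.** Applying 5.2.2 and 5.2.3 as written to four hypothetical patients:

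| Patient | FAS | Safety Population, read literally | In the stated safety analysis |
|---|---|---|---|
| Lipoic acid, stops for good in week 2 for an adverse event | no | yes | no |
| Placebo, stops for good in week 2 for an adverse event | no | no | no |
| Lipoic acid, dies before one month | no | yes | no |
| Either arm, adverse event in week 2, continues drug beyond one month | yes | yes on lipoic acid, no on placebo | yes |

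The rule removes patients, not a period of time. First-month events of those who continue are still analysed. For those who do not, events are recorded (sections 4.3 and 4.4) but fall outside the analysis set.

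The table applies the FAS duration condition to either capsule and the Safety Population wording literally.

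**Scale.** The protocol states no number of patients omitted, so there is no figure to reproduce. Inputs from 5.1: 150 per arm, 24 months, 5% withdrawal in both groups, 35% control event rate, HR 0.60.

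1. Planned withdrawals: 150 × 0.05 = 7.5 per arm over 24 months.
2. Spread at a constant rate, the month-1 probability is 1 − 0.95^(1/24) = 0.00213, and 150 × 0.00213 = 0.32 per arm.
3. If all planned withdrawals fell in month 1, the loss would be 7.5 per arm, or 15 of 300. This is an extreme case.
4. Drug can be stopped without withdrawing from follow-up, and the protocol gives no rate for that. With an assumed month-1 stopping rate of 1% to 5%: 150 × 0.01 = 1.5 to 150 × 0.05 = 7.5 per arm, or 3 to 15 of 300.
5. Early deaths add to this, and no mortality rate is given. A ceiling follows from the composite primary endpoint, assuming a constant hazard. The control hazard is h = −ln(0.65)/24 = 0.01795 per month. Expected first primary events in month 1 are 150 × (1 − exp(−h)) = 2.67 on control and 150 × (1 − exp(−0.6h)) = 1.61 on lipoic acid. Every death in month 1 is either one of these events or follows one, so expected deaths cannot exceed these figures under the planning assumptions. Heart failure rehospitalisation alone does not remove a patient who stays on drug.

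**The case against.** - **The placebo reading proves too much.** Section 3.4.1 calls only lipoic acid the investigational drug. Read just as literally, the FAS condition would then remove every placebo patient, although 5.2.3 plainly compares the two arms. The single label in 3.4.3 suggests that the drug name is used loosely for the blinded product. This stands: the omission of placebo is probably a drafting slip. It shows that the definition is ambiguous and needs rewording before use, and it is not the main point.
- **The figures do not bound the loss.** The 5% concerns withdrawal, whereas the FAS condition concerns duration of drug use. The all-early case is not suggested by anything in the protocol, and most primary events need not be deaths. This also stands, so the numbers give scale only.
- **A first-month stop is not always lost.** The protocol does not say that the month must be continuous, so a patient who interrupts and resumes may qualify. The loss therefore concerns permanent stops and deaths.
- **The practical effect may be small.** The background section puts adverse reactions to lipoic acid below 1/10,000, and adverse events are recorded for all subjects. Both are true, but recording an event does not place it in the comparison.

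None of this alters the main point: 5.2.3 places safety in a set that 5.2.2 conditions on a month of drug use.

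**Conclusion.** The concern holds. Followed exactly, the protocol compares safety in a selected group and leaves its own Safety Population without a purpose. Describing the FAS as intention to treat does not help, because the one-month condition is part of its definition. Nor is this a detail left open for the SAP: the protocol itself fixes both the sets and the assignment.

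The number omitted may be anywhere from under one patient per arm (constant-rate withdrawal only) to 7.5 per arm (5% stopping in month 1, an assumption), plus early deaths. No excess in either arm can be stated, and the number attributable to the drug may be small. With 150 per arm, however, a few early stops for adverse events can be an important part of the tolerability signal. It should be fixed. The effect of the same one-month condition on the primary endpoint is a separate matter and is not counted here.

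**What to change.** - In 5.2.2, define the safety set as all randomised patients who took at least one dose of study medication, lipoic acid or placebo, grouped by treatment received, whatever their duration of use and whether or not they are later found ineligible. The last condition is needed because the present wording also requires patients to meet the screening criteria, which would drop treated patients found afterwards not to qualify.
- In 5.2.3, state that safety is analysed in this set and not in the one-month FAS.

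The cost is two sentences. Telephone contact in months without a visit (3.5.2), case report form recording (4.3) and the 15-day follow-up of early leavers (4.4) already collect the events in both arms. No new data, visits or changes to treatment are required.

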3.5.2 Follow-up Period

Patients underwent baseline visits on Day 0 post-randomization, followed by visits at Months 6, 12, and 24, totaling 4 on-site visits for efficacy, compliance, and safety assessments until study completion. The follow-up period lasted 24 months.

Visit 1 (Screening and Enrollment Period)

Inclusion and exclusion criteria

Informed consent signing

Past medical history and comorbidities

Comprehensive physical examination

Detailed documentation of medical history, comorbidities, treatment, concomitant medications, blood pressure, heart rate, weight measurement.

Cardiac function assessment (6-minute walk test: 6MWD)

Electrocardiogram (ECG)

Echocardiography

Laboratory tests: blood/urine/biochemical parameters, brain natriuretic peptide (BNP), coagulation function

Distribution of study medication

Instructions for the next follow-up visit date and brief physical examination

Visit 2 (Month 6 post-randomization), Visit 3 (Month 12 post-randomization), Visit 4 (Month 24 post-randomization)

Heart failure symptoms and signs

Comprehensive physical examination

Blood pressure, heart rate, weight measurement

Documentation of primary and secondary endpoint events

Adverse event recording

Cardiac function assessment (6MWD)

ECG

Echocardiography

Laboratory tests (blood/urine/biochemical parameters, BNP), coagulation function

Distribution/collection of study medication

Instructions for the next follow-up visit date or study termination

During months without on-site visits, researchers should contact patients via telephone to inquire about adverse events, endpoint events, and changes in concomitant medications, completing corresponding records.

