3.6 Study Endpoint

3.6.1 Primary Endpoint:

A composite endpoint of all-cause death and rehospitalization due to heart failure during the 24-month follow-up period.

3.6.2 Secondary Endpoints:

The second endpoints included all-cause death and rehospitalization due to heart failure, non-fatal MI or non-fatal stroke during the 24-month follow-up period. The changes of LVEF and 6MWD were also assessed from baseline to 24 months.

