5.1 Sample Size Calculation

This pilot and feasibility study was designed to evaluate the efficacy and safety of ALA in IHF patients and get the reference data on outcomes related to clinical events for the future RCT with large sample size. As a feasibility trial, 300 patients were expected to be enrolled during the study period. Assumptions for sample size calculation included the following: the event rate for primary outcomes was 35% at 24 months in the control group[30]; the HR for the ALA group was estimated to be 0.60 and a withdrawal rate of 5% at 24 months in both groups. A total of 300 (150 per group) subjects followed up for a fixed period of 24 months provides 80% power to reject the null hypothesis at the two-sided 0.1 significance level.

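### The full analysis set is called intention-to-treat but requires one month of drug use, so month-1 deaths and early stoppers leave the primary analysis

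*Protocol*

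**What the plan says.** - **Analysis set.** Section 5.2.2 bases the primary and other endpoints on the FAS. It says the FAS follows the intention-to-treat principle, "with the additional condition that the investigational drug has been used for at least one month, allowing for reasonable exclusions".
- **Label repeated.** Section 5.2.3 states, without the one-month condition: "The analysis of safety and efficacy was performed in full analysis set (FAS) adhering to the intention-to-treat principle".
- **Time origin.** Section 5.2.3 has the cumulative incidence "expressed as Kaplan-Meier curves over 24 months after randomization", based on time to first event.
- **Endpoint.** Section 3.6.1: "A composite endpoint of all-cause death and rehospitalization due to heart failure during the 24-month follow-up period".
- **Withdrawal.** Section 3.2 lists grounds for withdrawal that include an intolerable adverse event and a participant who is "unable to adhere to the study protocol for treatment, demonstrates poor compliance".
- **After withdrawal.** Section 4.4: "For subjects who withdraw prematurely, safety follow-up will also be conducted 15 days after the end of the study visit". No endpoint follow-up is named there for these patients.
- **Planned contacts.** Section 3.5.2 has visits at months 6, 12 and 24. In months without a visit, "researchers should contact patients via telephone to inquire about adverse events, endpoint events, and changes in concomitant medications".
- **Purpose.** Section 5.1 says the trial is also meant to "get the reference data on outcomes related to clinical events for the future RCT with large sample size".

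**The concern.** Intention-to-treat means that everyone randomised is analysed in the arm assigned. A condition of one month of drug use makes membership of the set depend on survival and behaviour after randomisation. The primary comparison is then no longer between the randomised groups, whatever the label says.

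Two kinds of patient are lost: those who die in month 1, and those who stop capsules in month 1, a period that includes the dose escalation in 3.5.1. If early stopping differs by arm and is related to risk, the hazard ratio is biased. Event rates from this set, carried forward as intention-to-treat data, would also give the planned larger trial a month with no deaths in it.

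A second problem sits behind the first. If patients who stop early are treated as withdrawn and receive only the 15-day safety contact, their endpoint data may never be collected. Redefining the set afterwards could not bring those data back.

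**Working it through.** **1. The passages side by side**

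| Provision | Consequence for a month-1 death |
|---|---|
| 3.6.1: all-cause death over 24 months is an endpoint event | counts |
| 5.2.3: time runs from randomisation | counts, at the observed time |
| 5.2.2 and 5.2.3: intention-to-treat | patient is in the set |
| 5.2.2: at least one month of drug use | patient is not in the set, so the death cannot count |

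The fourth row contradicts the other three. A month-1 heart failure rehospitalisation is different: it still counts if the patient goes on to complete a month of capsules. The other sets in 5.2.2 (safety and per-protocol) do not restore an all-randomised analysis of the primary endpoint. Section 3.4.1 lists lipoic acid as the investigational drug and placebo separately, so the text does not even make clear that the one-month rule applies to both arms, although that is the natural reading.

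**2. Events in month 1**

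The protocol gives no figure for month 1, so this uses its planning inputs (5.1): 150 per arm, 35% control rate at 24 months, HR 0.60. Constant hazard is assumed, without dropout.

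- Control hazard: −ln(0.65)/24 = 0.01795 per month. ALA: 0.6 × 0.01795 = 0.01077.
- Month-1 events: 150 × (1 − e^(−0.01795)) = 2.67 control; 150 × (1 − e^(−0.01077)) = 1.61 ALA; sum 4.28.
- 24-month events: 52.5 + 34.2 = 86.7. Share in month 1: 4.28/86.7 = 4.9%.
- The protocol does not say what share are deaths. At an assumed 20–50%, the loss is 0.2 × 4.28 = 0.9 to 0.5 × 4.28 = 2.1 events. Losing them in both arms leaves the HR about unchanged.

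**3. Bias from removing early stoppers**

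The documents give no month-1 stopping rate by arm. Assume no drug effect, and a fraction f of patients with k times the hazard of the rest, who are the ones who stop in month 1. The hazard λ of the rest solves (1 − f)e^(−24λ) + f e^(−24kλ) = 0.65. The HR is the large-sample Cox value.

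| f, k | Stoppers removed, ALA only | ALA stoppers kept but censored at 0.25 / 0.5 / 1 month |
|---|---|---|
| 1%, 1.5 | 0.9955 | 0.9955 / 0.9956 / 0.9957 |
| 1%, 2 | 0.9918 | 0.9919 / 0.9920 / 0.9923 |
| 2%, 1.5 | 0.9910 | 0.9911 / 0.9912 / 0.9915 |
| 2%, 2 | 0.9837 | 0.9839 / 0.9842 / 0.9847 |

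Hand check for 2%, 2: with x = e^(−24λ), 0.98x + 0.02x² = 0.65 gives x = 0.6545. The ratio of 24-month cumulative hazards is ln(0.6545)/ln(0.65) = 0.984.

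Removal from placebo only gives 1.0045 (1%, 1.5) to 1.0166 (2%, 2). Equal removal in both arms gives 1.000.

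False-claim rate: with no effect, 300 × 0.35 = 105 events, so the SE of log HR is 2/√105 = 0.195. At z < −1.96, HR 0.996 gives 2.6% and HR 0.984 gives 3.0%, against 2.5% one-sided.

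**4. Changing the set without following stoppers**

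The last column of the table shows that keeping stoppers but censoring them within month 1 leaves 94–99% of the bias on the log-HR scale. For f = 2%, k = 2, with those not followed censored at 0.5 month:

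| Share of stoppers followed to month 24 | HR |
|---|---|
| 0% | 0.984 |
| 50% | 0.992 |
| 80% | 0.997 |
| 90% | 0.998 |
| 100% | 1.000 |

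**The case against.** The strongest objection is that the likely harm is small. The trial is double-blind, patients are stable on fixed treatment, the background calls adverse reactions extremely rare, and the trial is an exploratory pilot. The only dropout figure is 5% withdrawal over 24 months in both groups; spread evenly, that is 5%/24 = 0.2% a month, well below the 1–2% assumed here. All of this stands, and it is why no large bias is claimed. It does not reconcile the two statements in 5.2.2, and nothing in the protocol rules out stopping that differs by arm.

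Second, the phrase about reasonable exclusions may describe the purpose of the one-month condition and not grant a further power to exclude. That is a fair reading. The wording is ambiguous, and the point does not depend on it.

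Third, 4.4 concerns safety follow-up and does not say that endpoint follow-up ends, while the monthly calls in 3.5.2 are not limited to patients on treatment. So it is not certain that stoppers would be censored. But 3.2 makes poor compliance and intolerable adverse events grounds for withdrawal, and nothing then says that endpoint data are still collected. The protocol should settle this.

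Fourth, 4.9% bounds the events lost through early death only under constant hazard. With an early hazard two or three times the average in both arms, month 1 would hold 8.5 or 12.6 events.

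Finally, a separate statistical analysis plan might add an all-randomised sensitivity analysis. That would not correct the primary set fixed here.

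**Conclusion.** The concern holds. The primary analysis set is not intention-to-treat as written: it excludes every month-1 death and every month-1 stopper, while the endpoint and the time origin require them to be counted. This follows from the text and needs no assumption.

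The size does rest on assumptions: planning rates and constant hazard for the 4.9% of events in month 1, and assumed stopping rates and risks for the HR of 0.996–0.984. Within those ranges the bias is small, it reverses direction if stoppers leave only the placebo arm, and it vanishes if stopping is equal in both arms. The point must still be fixed, because it lies in the definition of the primary analysis set and because endpoint data not collected from early stoppers cannot be recovered later.

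**What to change.** 1. In 5.2.2, replace the FAS definition with: all randomised patients, analysed in the arm assigned, from randomisation to month 24. Remove the one-month condition and the exclusion phrase attached to it, together with the remainder of that sentence, which would otherwise be left hanging. Section 5.2.3 then needs no change on this point.
2. Keep the one-month set, if wanted, as a supplementary analysis under its own name, and state that it covers capsules of either arm.
3. Reconcile 3.2, 3.5.2 and 4.4: distinguish stopping capsules from withdrawing from the study, and state that endpoint data are collected to month 24 from patients who stop capsules but do not withdraw consent, through the visits and monthly calls already in 3.5.2. This concerns data collection only and leaves the rules for stopping capsules untouched.

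The cost is one redefined set and matching wording in three sections, a slight dilution of the effect by early stoppers, and continued contact with them. At the assumed 1–2% of 300, that is 3–6 patients.
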